2.1. Multiplicity Adjustment

Since they are intended for different purposes, no type I error rate adjustments will be made for conducting analyses relative to “efficacy” and “treatment-regimen” estimands. For analyses within each estimand, the type I error control strategy for evaluation of primary and key secondary objectives is illustrated in [Figure GPIM.2.1](#).

1. $H_{15,1}$, $H_{15,2}$, are evaluated hierarchically each at a 2-sided 0.025 significance level conditioned on successfully achieving the preceding objective. In parallel,
2. $H_{10,1}$, $H_{10,2}$ are evaluated hierarchically each at two-sided 0.025 significance level conditioned on successfully achieving the preceding objective.
3.
 - a) If all objectives in #1 and #2 above are successfully established, $H_{5,1}$, $H_{5,2}$ are evaluated hierarchically, each at a 2-sided 0.05 significance level.
 - b) If all objectives in only #1 or only #2 above are successfully established, $H_{5,1}$, $H_{5,2}$ are evaluated hierarchically, each at a 2-sided 0.025 significance level.
4. If all objectives: $H_{5,1}$, $H_{5,2}$ are successfully established and
 - a) if all objectives in #1 and #2 above are successfully established, then $H_{15,3}$, $H_{10,3}$, $H_{5,3}$, $H_{15,4}$, $H_{10,4}$, $H_{5,4}$, $H_{15,5}$, $H_{10,5}$, $H_{5,5}$, $H_{15,6}$, $H_{10,6}$ and $H_{5,6}$ will be evaluated hierarchically each at two-sided 0.05 significance level conditioned on the successfully achieving the preceding objective.
 - b) If all objectives in only #1 or only #2 above are successfully established, then $H_{15,3}$, $H_{10,3}$, $H_{5,3}$, $H_{15,4}$, $H_{10,4}$, $H_{5,4}$, $H_{15,5}$, $H_{10,5}$, $H_{5,5}$, $H_{15,6}$, $H_{10,6}$ and $H_{5,6}$ will be

- c) evaluated hierarchically each at a 2-sided 0.025 significance level conditioned on successfully achieving the preceding objective.

5. If all objectives in #3 and #4 above are successfully established, and at least 1 objective from #1 or #2 above is not successfully established, recycle 100% of the unused alpha back to #1 or #2 above.

[figure not shown]

Figure GPIM.2.1

Type I Error control strategy for primary and key secondary efficacy endpoints.

3. Analysis Sets

Table GPIM.3.1 defines the analysis population and datasets for the purposes of analysis based on the estimands defined in Section 1.1.

Table GPIM.3.1. Analysis Populations/Data Sets

Population/Analysis Set	Description
Screened population	All participants who signed informed consent.
Randomized population	All participants who are randomly assigned to a treatment group.
Modified intent-to-treat population (mITT)	All randomly assigned participants who are exposed to at least 1 dose of study intervention. Participants will be analyzed according to the treatment they were randomly assigned to regardless of the treatment actually received.
Efficacy Analysis Set: This analysis set will be used to estimate the efficacy estimand for the primary and key secondary objectives	Data obtained during the Treatment Period from the mITT population, excluding participants discontinuing study drug due to inadvertent enrollment, excluding data after permanent discontinuation of treatment or initiation of antihyperglycemic rescue medication.
Full Analysis Set: This analysis set will be used to estimate the treatment-regimen estimand for the primary and key secondary objectives	Data obtained during the treatment period from the mITT population, excluding participants discontinuing study drug due to inadvertent enrollment, regardless of adherence to treatment or initiation of antihyperglycemic rescue medication.
Safety Analysis Set (SS): This analysis will be used to assess the safety of study treatment	Data obtained during the Treatment Period plus Safety Follow-Up from the mITT population, regardless of adherence to treatment or initiation of antihyperglycemic rescue antihyperglycemic medication.

4. Statistical Analyses

4.1. General Considerations

Statistical analysis of this study will be the responsibility of Eli Lilly and Company (Lilly) or its designee. The statistical analyses will be performed using SAS® (Version 9.4 or higher) and R® (Version 4.3.2 or higher).

Any change to the data analysis methods described in the protocol will require an amendment ONLY if it changes a principal feature of the protocol. Any other change to the data analysis methods described in the protocol, and the justification for making the change, will be described in the statistical analysis plan or clinical study report. Some analyses and summaries described in this analysis plan may not be conducted if not warranted by data (for example, few events to justify conducting an analysis). Listings of events will be provided in such situations. The primary analysis will be performed at database release after Last Participant Last Visit (LPLV). Additional analyses of the data may be conducted as deemed appropriate without further changes made to the protocol or SAP, even after the primary or final database locks.

Additionally, to avoid potential selection biases, unless stated otherwise, statistical summaries and analyses will be conducted based on randomized maintenance dose regardless of the actual treatment received by the patient.

Unless specified otherwise, the last measurement during Visit 1 to Visit 3 (including unscheduled visits) collected prior to or on the first dose day will serve as baseline.

- For lab and ECG, baseline needs to be prior to or within one hour after the first dose time.
- For patient-reported outcomes, data collected at Visit 3, regardless of the timing relative to first dose, will serve as baseline.

All tests of treatment effects will be conducted at a 2-sided alpha level of 0.05, unless otherwise stated, and all confidence intervals will be given at a 2-sided [95%] level. To avoid potential selection biases, unless stated otherwise, in statistical summaries and analyses, all data will be analyzed by randomized treatment assignment.

There will be 2 estimands of interest in evaluating the primary and secondary efficacy objectives. The first estimand, the “efficacy” estimand, represents efficacy prior to discontinuation of study drug without the confounding effects of rescue therapy for severe persistent hyperglycemia. Analyses relative to the “efficacy” estimand will be conducted using the efficacy analysis set (EAS). The second estimand, the “treatment-regimen” estimand, represents the efficacy irrespective of adherence to investigational product or introduction of rescue therapy for severe persistent hyperglycemia. Analyses relative to the “treatment-regimen” estimand will be conducted using the full analysis set (FAS).

Safety will be assessed using Safety Analysis Set. Selected safety analyses may be conducted after excluding data on rescue therapy or data after starting another antihyperglycemic medication.

A listing of patients randomized but not included in efficacy analyses (not treated or discontinued treatment due to inadvertent enrollment) will be provided.

End of study participation for a patient will be the earliest of date of death, date of withdrawal from further participation in the study, or date of safety follow up visit (Visit 801). For patients considered to be lost to follow-up, end of study participation will be the date of lost to follow-up reported by the investigator. Patient data included in the database after the last date of study participation (date of death, date of early discontinuation or date of safety follow-up) will be excluded from statistical analysis. Listings of such data may be provided.

Summary statistics for continuous measures may include sample size, mean, standard deviation, median, minimum, and maximum.

The Kaplan-Meier method may be used for estimation of cumulative event-free survival rates over time, and Cox proportional hazards regression analysis will be used to compare hazard rates among treatments.

Summary statistics for categorical measures, including categorized continuous measures, will include sample size, frequency, and percentages. Fisher's exact test will be used to examine the treatment difference in categorical outcomes. Logistic regression may be used to examine the treatment difference in binary efficacy outcomes. The negative binomial regression model will be used for the treatment comparison of discrete count measures if deemed appropriate.

Statistical treatment comparisons will only be performed between tirzepatide doses and placebo. Comparisons among tirzepatide arms will not be performed unless specified otherwise.

Statistical summaries and results of statistical analyses will be displayed in the following treatment order: tirzepatide 5 mg, tirzepatide 10 mg, tirzepatide 15 mg, placebo.

4.2. Participant Dispositions

Reasons for screen failures as reported by investigators will be summarized.

A listing of final study disposition and a listing of randomized treatment assignment (planned treatment) for all randomized patients will be provided. The number and percentage of participants prematurely discontinuing study treatment and study will be provided by study treatment. Reasons for prematurely discontinuing study treatment and study will be provided by study treatment.

4.3. Primary Endpoint(s) Analysis

4.3.1. Definition of endpoint(s)

The primary endpoint for this study is mean HbA1c change from baseline at 40 weeks. This endpoint will be used to evaluate the primary objective of the study for both the treatment-regimen and the efficacy estimands (Section 1.1).

The primary efficacy measure will be change in HbA1c (%) and mmol/mol) from baseline (postbaseline – baseline). Both HbA1c values as well as change from baseline in HbA1c will be summarized by treatment and nominal visit (week). If scheduled HbA1c data at the primary endpoint visit is not available, unscheduled HbA1c data collected for the primary endpoint visit will be included in the analysis.

4.3.2. Primary Analysis Relative to the Efficacy Estimand

The primary analysis relative to the “efficacy” estimand will be conducted using HbA1c data in the EAS from baseline through the 40 -week visit with the aid of a mixed-model repeated measure (MMRM). Restricted maximum likelihood (REML) will be used to obtain model parameter estimates and the Kenward-Roger option will be used to estimate denominator degrees of freedom. The response variable of the MMRM model will be change in HbA1c values from baseline obtained at each scheduled postbaseline visit. The independent variables of the MMRM model are treatment, visit, treatment-by-visit interaction, SGLT-2i use (Yes or No) as fixed effects, and baseline HbA1c as covariates. Missing data will be addressed by the MMRM model. No explicit imputation methods for missing data will be employed. An unstructured covariance matrix will be used to model the within-patient errors. If this model fails to converge, the following covariance structures will be tested in the following order:

1. Heterogeneous Toeplitz
2. Heterogeneous First Order Autoregressive
3. Heterogeneous Compound Symmetry
4. Toeplitz
5. First Order Autoregressive, and
6. Compound Symmetry.

The first covariance structure that converges will be used. The resulting least squares mean (LSM) estimate of mean change from baseline in HbA1c will be summarized by visit and by study treatment.

With the aid of the MMRM analysis, p-values, and 2-sided 95% confidence intervals (CIs) for mean change in HbA1c from baseline to the 40-week visit will be derived and summarized for the 5 mg, 10 mg, and 15 mg doses of tirzepatide compared to placebo.

4.3.3. Primary Analysis Relative to the Treatment-Regimen Estimand

The primary analysis relative to the treatment-regimen estimand will be conducted utilizing HbA1c data in the FAS at baseline and at the 40-week visit with the aid of an ANCOVA model. The response variable will be the primary measure and model terms will include treatment, SGLT-2i use (Yes or No) as fixed effects and baseline HbA1c as a covariate. The ANCOVA analysis will be conducted using multiple imputation of missing primary measures (see Section 4.3.4 for details) and statistical inference over multiple imputation of missing data guided by Rubin (1987). With the aid of the ANCOVA analysis, p-values and 2-sided 95% CIs for mean change in HbA1c from baseline to the 40-week visit will be derived and summarized for the 5 mg, 10 mg, and 15 mg doses of tirzepatide compared to placebo.

4.3.4. Methods for Multiple Imputations

For efficacy analyses relative to the “treatment-regimen” estimand, missing HbA1c data at the 40-week visit will be imputed based on “retrieved dropouts,” defined as patients who had their HbA1c value measured at the 40-week visit in the same treatment arm who prematurely

discontinued study drug. A pseudo-SAS program for implementing multiple imputations using data from retrieved dropouts is included in Section 7.1 (Appendix 1). In cases where there are not enough retrieved dropouts (i.e. for any group with ≤ 4 discontinued patients who have data recorded at the 40-week visit) to provide a reliable imputation model, an alternative multiple imputation method with reference to the placebo group (placebo multiple imputation) will be used as the primary analysis relative to the treatment-regimen estimand. Analyses will be conducted with multiple imputations, and statistical inference over multiple imputations will be guided by the method proposed by Rubin (1987). If the primary analysis using “retrieved dropouts” for imputation converges, the analysis using “placebo multiple imputation” to impute the missing data will be conducted as a sensitivity analysis. If value of the imputed HbA1c change from baseline is $<-6.0\%$ or $>6.0\%$, that value will be set to -6.0% or 6.0% , respectively, to avoid unrealistic imputed values.

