The following changes in study conduct will not be considered protocol deviations.

Remote visits***Types of remote visits*****Telemedicine:**

Telephone or technology-assisted virtual visits, or both, are acceptable to complete appropriate assessments. Assessments to be completed in this manner include, but are not limited to, medical history, AEs and product complaints, concomitant medications, diabetes education, reminding 7-point SMBG, reviewing insulin dose and adjustment per TTT algorithm, assessing compliance with insulin dose adjustment TTT algorithm, reviewing diary.

Other alternative locations:

Laboratory testing in local hospital is permitted based on the discretion of investigator with the approval of sponsor.

Data capture

In source documents and the CRF, the study site should capture the visit method, with a specific explanation for any data missing because of missed in-person site visits.

Safety reporting

Regardless of the type of remote visits implemented, the protocol requirements regarding the reporting of adverse events (AEs), serious adverse events (SAEs), and product complaints remain unchanged.

Return to on-site visits

Every effort should be made to enable participants to return to on-site visits as soon as reasonably possible, while ensuring the safety of both the participants and the site personnel.

Local laboratory testing option

Local laboratory testing may be conducted in lieu of central laboratory testing. However, central laboratory testing must be retained for: HbA1c and FSG at Visit 3 and Visit 19. The local laboratory must be qualified in accordance with applicable local regulations. Clinically significant laboratory findings could be recorded as an AE in the AE CRF at the discretion of investigator.

Study intervention and ancillary supplies (including participant diaries)

When a participant is unable to go to the site to receive study supplies during normal on-site visits, the site should work with the sponsor to determine appropriate actions. These actions may include:

- asking the participant to go to the site and receive study supplies from site personnel without completion of a full study visit,
- asking the participant's designee to go to the site and receive study supplies on a participant's behalf,
- arranging delivery of study supplies.

These requirements must be met before action is taken:

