- *Population-level summary:* Difference in mean changes between treatment conditions.

Secondary estimand

The treatment-regimen estimand answers the following question of interest for the primary objective: What is the treatment difference in change from baseline in HbA1c after 40 weeks of treatment in participants with T2DM regardless of treatment discontinuation for any reason and regardless of initiation of antihyperglycemic rescue?

The treatment-regimen estimand is described by the following attributes.

[figure not shown]
- *Population:* Participants with T2DM inadequately controlled on insulin glargine alone or in combination with metformin with or without SGLT-2i.
- *Endpoint:* Change from baseline to week 40 after randomization in HbA1c.
- *Treatment condition:* The randomized treatment regardless of adherence to treatment with or without antihyperglycemic rescue medication.
- *Intercurrent events:* “Permanent discontinuation from treatment for any reason” and “initiation of rescue antihyperglycemic treatment” are addressed by the treatment condition.
- *Population-level summary:* Difference in mean changes between treatment conditions.

Both the efficacy and treatment-regimen estimands will be evaluated for the primary and all key secondary objectives. The population, treatment condition, and intercurrent events specified above for each estimand for the primary objective will also apply to the key secondary objectives. The endpoint for each key secondary objective is defined in the table above.

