4.10. Changes to Protocol-Planned Analyses

NA

5. Sample Size Determination

Participants will be randomized in a 1:1:1:1 ratio to tirzepatide 5 mg, 10 mg, 15 mg, or placebo. The trial is powered to assess superiority of tirzepatide 10 mg and 15 mg, each tested in parallel, against placebo at a 2-sided significance level of 0.025, relative to the primary endpoint (mean change in HbA1c from baseline to 40 weeks), under the following assumptions: use of a 2-sample t-test utilizing HbA1c data collected before initiation of any rescue medication or premature treatment discontinuation with no more than 25% of participants initiating rescue medication or prematurely discontinuing treatment in each treatment group; 0.95% greater mean reduction in HbA1c from baseline for 10 and 15 mg tirzepatide compared with placebo; 1:1:1:1 randomization; and a common standard deviation (SD) of 1.3%. On the basis of these assumptions, a sample size of 256 participants is required to ensure at least 90% power to demonstrate that tirzepatide 10 mg and/or 15 mg are superior to placebo relative to the primary endpoint.

Assignment to treatment arms will be determined by a computer-generated random sequence using an interactive web response system (IWRS). Patients will be randomized in a 1:1:1:1 ratio to receive 5 mg tirzepatide, 10 mg tirzepatide, 15 mg tirzepatide, or placebo. The randomization will be stratified by baseline HbA1c concentration ($\leq 8.0\%$, $> 8.0\%$ [≤ 64 , > 64 mmol/mol]), and SGLT-2i use (Yes/No).

6. Supporting Documentation

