7.1. Appendix 1. SAS Code for Multiple Imputation

```
*retrieved dropout imputation*;
*ret_flg is a flag variable for subjects that are retrieved dropouts*;
proc mi data=&dataset_in. seed=&seed. out=&dataset_out. nimpute=&n_impute. ;
by trtpn;
class ret_flg;
monotone reg(chg/details);
mnar model (chg/modelobs=(ret_flg='Y'));
var base chg;
run;

*placebo imputation*;
*replace 'placebo' with the assigned value for the placebo group*;
proc mi data=&dataset_in. seed=&seed. out=&dataset_out_2. nimpute=&n_impute. ;
class trtpn;
monotone reg(chg/details);
mnar model (chg/modelobs=(trtpn='placebo'));
var base chg;
run;
```

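### The treatment-regimen imputation ignores whether the participant being imputed is still on study drug, so an adherent tirzepatide participant with no Week 40 sample is imputed as if not on tirzepatide

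*SAP*

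**What the plan says.** - **Estimand.** SAP 1.1 gives the treatment condition of the treatment-regimen estimand as "The randomized treatment regardless of adherence to treatment with or without antihyperglycemic rescue medication". Stopping drug and starting rescue are both absorbed into that condition.
- **Main rule.** SAP 4.3.4 states that "missing HbA1c data at the 40-week visit will be imputed based on" retrieved dropouts, meaning participants in the same arm who stopped study drug early but were measured at Week 40.
- **Code.** The first block of SAP Appendix 1 runs by arm and fits the model only to flagged retrieved dropouts ("mnar model (chg/modelobs=(ret_flg='Y"). Its variable list holds baseline and change only. Nothing selects which missing records are filled.
- **Fallback.** With four or fewer retrieved dropouts in any group, SAP 4.3.4 moves to imputation from the placebo arm. The second code block does this, again whatever the drug status of the participant with the gap.
- **Reach.** SAP 4.4.1.2 and 4.4.1.3 carry the method to body weight and FSG. In 4.4.1.4 the HbA1c target indicators are cut from the imputed HbA1c values. Protocol 9.3.3 says only that multiple imputation will be used.
- **Remote visits.** Protocol Appendix 8 (10.8) allows remote visits and local laboratories in exceptional circumstances, but "central laboratory testing must be retained for: HbA1c and FSG at Visit 3 and Visit 19".

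**The concern.** The donors are defined by having stopped drug; the recipients are everyone with a gap. The two match when the recipient has also stopped. They do not match when the recipient is still injecting and the Week 40 sample failed, was not drawn, or could not be taken at a remote visit.

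Take a hypothetical 15 mg participant who has taken every dose, has HbA1c 6.3% at Week 32 and has no Week 40 sample. The estimand wants this person's outcome under the adherence that occurred, which is full adherence. The stated rule draws it from people who stopped tirzepatide or, under the fallback, from placebo, and it does not use the Week 32 value. Participants on add-on rescue who remain on study drug (Protocol 8.3.4.2) are in the same position.

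In the tirzepatide arms this replaces on-drug outcomes by off-drug ones. In the placebo arm the swap should change little. The error therefore does not cancel, and the treatment-regimen difference moves toward zero. Those analyses carry their own family-wise error control of 0.05 (Protocol 9.3.4, SAP 2.1), so they are more than descriptive.

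**Working it through.** **1. The plan's own figure.** Inputs from SAP Section 5 (Sample Size Determination): two-sided 0.025 per comparison ("each tested in parallel, against placebo at a 2-sided significance level of 0.025"), "0.95% greater mean reduction in HbA1c from baseline for 10 and 15 mg tirzepatide compared with placebo", "a common standard deviation (SD) of 1.3"%, at most 25% lost to rescue or discontinuation, and "a sample size of 256 participants is required to ensure at least 90% power". The Protocol synopsis gives 64 per arm.
- Evaluable per arm: 64 × 0.75 = 48.
- SE = 1.3 × √(2/48) = 0.265; noncentrality = 0.95/0.265 = 3.58.
- Exact noncentral-t power = 0.902. The smallest n per arm giving 90% is 48; 48/0.75 = 64; 4 × 64 = 256.

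The stated size reproduces and is not in question. It supplies the 64 and the 0.95 used below.

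**2. Donors against recipients.**

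| Participant with no Week 40 value | What the estimand asks for | Main-rule donors | Fallback donors |
|---|---|---|---|
| Stopped tirzepatide | outcome after stopping | same-arm stoppers: match | placebo arm |
| Still on tirzepatide | outcome on tirzepatide | same-arm stoppers: mismatch | placebo arm: mismatch |

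No stated route fills the second row from on-drug participants.

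**3. Size of the shift.** Let m be the number per tirzepatide arm still on drug with no Week 40 value, and L the effect lost by imputing them as off drug. Assume the placebo mean does not move. Then

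shift = (m/64) × L.

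Neither m nor L is in the documents. Assumed ranges: m = 1, 3, 5; L = 0.95 (all lost) or 0.475 (half lost).

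| m | m/64 | Shift, all lost | Shift, half lost |
|---|---|---|---|
| 1 | 1.6% | 0.015 | 0.007 |
| 3 | 4.7% | 0.045 | 0.022 |
| 5 | 7.8% | 0.074 | 0.037 |

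With 64 per arm and SD 1.3 the SE of a difference is 1.3 × √(2/64) = 0.230, so the all-lost shifts are about 0.06, 0.19 and 0.32 SE. Under the placebo fallback the all-lost column applies.

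**4. Precision (illustrative only).** A few donors must also fill more gaps. A simulation (64 per arm, 20 imputations, Rubin's rules, 1,000 runs, no effect retained off drug) put three on-drug participants with missing values in each arm. With 5 retrieved dropouts and 3 missing discontinuers per arm, the SE was 0.301 under the SAP rule and 0.269 with donors matched on drug status. With 8 and 4, it was 0.281 against 0.264. All these counts are assumed. Five is the smallest donor count that avoids the fallback, so the first pair is close to the worst case.

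**5. Which donors would apply.** This too depends on assumed rates. The chance that at least one of four arms has four or fewer retrieved dropouts is 99.8% if 10% discontinue and half of them are retrieved, 30% at 25% and half, and 3% at 25% and 70%. Either route may therefore be the one used.

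**The case against.** The strongest reply is that the case should be rare and its effect small.

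- Leaving the study entails stopping drug (Protocol 7.2), so most missing Week 40 values should belong to people already off drug, whom the rule fits.
- An unscheduled HbA1c collected for the endpoint visit replaces a missing scheduled one (SAP 4.3.1).
- Appendix 8 keeps central HbA1c and FSG at Visit 19 and widens that visit's window to 14 days before and 28 days after, in order to limit missing data.
- Retrieved dropouts may have stopped late, and they receive other glucose-lowering treatment (Protocol 7.1.1), so total loss of effect is an upper bound under the main rule.
- The direction is conservative for tirzepatide, and the estimand concerned is the secondary one.
- The SAP calls its code a pseudo-program, so a filter could sit upstream.

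All of this stands as to frequency and size. It does not remove the mismatch: no filter is stated, and a conservative direction does not make an estimate answer its question.

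Three stronger readings are tempting but unsupported. A reader might infer that every gap is filled from drug stoppers; under the fallback the donors are the placebo arm, adherent participants included. A reader might infer that Appendix 8 creates the missingness; its provisions try to prevent it, and a Visit 19 with no central sample is only a residual possibility. A reader might infer that the primary result is biased; SAP 4.3.2 uses an MMRM over all scheduled post-baseline visits with no explicit imputation, so this rule does not enter it.

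**Conclusion.** The point holds as a mismatch between the stated imputation rule and the treatment-regimen estimand, for HbA1c, body weight, FSG and the HbA1c targets. On the planned 0.95-point HbA1c difference the attenuation is at most 0.015 to 0.074 points for 1 to 5 affected participants per arm, and about half that if off-drug participants keep half the effect. This rests on three assumptions that the documents do not settle: the number affected, the effect retained after stopping, and a placebo mean that does not move. The likely count is low, so this is worth correcting because the correction is cheap. It does not threaten the trial's main conclusion. The sample size and the primary efficacy analysis are unaffected.

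**What to change.** In SAP 4.3.4 and Appendix 1, split missing Week 40 values by study-drug status.

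- **(a)** For participants who permanently discontinued study drug, withdrew, were lost to follow-up or have unknown drug status, keep retrieved-dropout imputation, or the placebo fallback. Lost and unknown cases belong here so that nobody is presumed adherent.
- **(b)** For participants documented as still on study drug in the Week 40 visit window, impute from same-arm participants on study drug at Week 40, using baseline and earlier post-baseline values. Fill intermittent gaps first.

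Add an on-drug flag to the code. Apply the same split to body weight and FSG, and derive the HbA1c targets from the resulting values.

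Cost: one more imputation step (two procedure calls where earlier visits have gaps), using study-drug disposition data already collected, and an analysis slightly less conservative for the few on-drug gaps. Protocol 9.3.3 names only multiple imputation, and Protocol 9.3.1 requires an amendment only for a principal feature, so a SAP revision before unblinding should be enough. If no on-drug value is missing, the result does not change.
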